1.1 Background

Barrett's Esophagus (BE) is the precursor lesion for the development of esophageal adenocarcinoma (EAC). BE is defined as the presence of intestinal metaplasia in the distal esophagus, and is associated with a 25-30 times increased risk of EAC.¹ Unfortunately, the prognosis of esophageal cancer is poor, with 5-year survival rates of 16.5% in the US.²

The development of BE is thought to be caused in part by acid reflux. The change in esophageal lining presumably develops as a result of chronic exposure to refluxed stomach acid and bile, leading to recurrent mucosal injury.³

Current management of BE patients consists of endoscopic surveillance and acid suppression.⁴ In theory, gastric acid suppression reduces chronic inflammation within the BE segment, which in turn may reduce the risk of progression to EAC.

By inhibiting acid secretion and increasing intragastric pH, proton pump inhibitors (PPIs) at therapeutic doses can cause secondary hypergastrinemia. Gastrin exerts trophic effects in BE via cholecystokinin-2 receptor (CCK2R) activation⁵, and there is some evidence that hypergastrinemia is associated with an increased risk of progression to high grade dysplasia and cancer.⁶

YF476 is a potent, orally active, highly selective, competitive antagonist of CCK2 receptors.⁷ The primary hypothesis for this study is that administration of YF476 to patients with BE will result in a significant decrease in cellular proliferation in the Barrett's mucosa.

1.2 Trial medication

YF476 (25 mg) or matching placebo: one capsule to be taken by mouth once daily for 12 weeks. Study medication will be taken with breakfast except on clinic visit days, when patients will fast overnight and take study medication after completion of study procedures.

1.3 Objectives

Primary:

The primary objective of this study is to determine if administration of YF476 (a CCK2R antagonist) to patients with Barrett's esophagus (BE) decreases tissue Ki67 expression, a marker of cellular proliferation.

Secondary:

The secondary objectives are to assess the effects of YF476 on:

- Biomarkers potentially associated with esophageal adenocarcinoma, in particular, cyclooxygenase-2 (COX-2), p53, CCK2R and DCAMKL1; and
- fasting serum gastrin, a marker of gastric acid suppression, and plasma chromogranin A (CgA), a marker of ECL cell hyperplasia.

We also aim to determine whether YF476 is safe in patients with BE.

1.4 Type of trial

Phase II, randomised, double-blind, out-patient trial.

1.5 Trial population

a **Total** 20 patients completing the trial.

b **Inclusion criteria**

1. Aged ≥ 18 years, with histologically confirmed diagnosis of BE without dysplasia. A prior endoscopy with biopsies read as indefinite for dysplasia is permitted if biopsies from the most recent endoscopy prior to study entry demonstrated BE without dysplasia.
2. Minimum of 1 cm circumferential Barrett's mucosa on endoscopy or at least 2 cm maximal contiguous extent of Barrett's mucosa. (Prague criteria $C \geq 1$, any M or any C, $M \geq 2$).
3. Proton pump inhibitor use at least once daily, for at least twelve months prior to enrollment, and stable dose of PPI for the three months before enrollment. Any PPI, dose, and frequency are allowable.
4. ECOG performance status ≤ 2 and Karnofsky $\geq 60\%$; see Appendix A.
5. Normal organ and marrow function, defined as white blood cells (WBC) $\geq 3 \times 10^9/L$, absolute neutrophil count $\geq 1.5 \times 10^9/L$, platelets $\geq 100 \times 10^9/L$, creatinine ≤ 1.5 mg/dL, total bilirubin ≤ 1.5 mg/dL, AST ≤ 100 U/L, ALT ≤ 100 U/L.
6. Use of adequate contraception during the study as follows.
 - Pre-menopausal women must use a highly effective method of contraception ($\leq 1\%$ failure/year when used correctly), including:
 - intrauterine device (IUD);
 - bilateral tubal occlusion;
 - vasectomised partner – must have had medical assessment of successful surgery;
 - intrauterine hormone-releasing system (IUS);

- progestogen-only hormonal contraception implants associated with inhibition of ovulation; or
 - hormonal contraception associated with inhibition of ovulation (combined or progestogen-only – includes oral, intravaginal, transdermal and injections).
 - To prevent pregnancy, men with partners of childbearing potential must use a condom or have had a vasectomy (with a medical assessment of successful surgery). Partners who are not of childbearing potential are defined as: men; post-menopausal women (no menstrual periods for at least 1 year); or women who have no uterus, ovaries or fallopian tubes.
 - Women classed as post-menopausal (no menstrual periods for at least 1 year) are not required to use contraception.
7. Willingness to comply with all treatment and follow-up procedures.
 8. Ability to understand and the willingness to sign a written informed consent document.
 9. Up to date with all age-appropriate cancer screening tests (based on national guidelines).

d Exclusion criteria

1. Histologically confirmed BE with high-grade dysplasia.
2. Histologically confirmed diagnosis of invasive carcinoma of the esophagus.
3. Histologically confirmed BE with low-grade dysplasia that has been diagnosed by at least two expert gastrointestinal pathologists.
4. Prior endoscopic therapy for Barrett's esophagus.
5. A relevant history of esophageal or gastric surgery that, in the investigator's opinion, could compromise the objectives of the trial.
6. History of atrophic gastritis, pernicious anemia, or Zollinger-Ellison syndrome.
7. Participation in a trial of an IMP within the previous 28 days.
8. Prolonged QTc interval >450 msec
9. History of allergic reactions attributed to compounds of similar chemical composition to YF476.
10. History or baseline findings of:
 - diabetes mellitus requiring insulin therapy;
 - pancreatitis (baseline amylase and/or lipase $\geq 2.0 \times$ ULN);
 - hepatitis B or hepatitis C;

- HIV, unless, at the discretion of the PI, with at least 120 days on stable antiretroviral therapy (ART) with undetectable HIV viral load and CD4 >350 cells/mm³;
 - malabsorption syndrome or inability to swallow or retain oral medicine;
 - major surgery ≤28 days prior to enrollment;
 - ECOG performance status ≥2; or
 - another cancer within 3 years except for basal carcinoma of the skin or cervical carcinoma in-situ.
 - Also, any clinically significant and uncontrolled major morbidity including but not limited to: serious cardiac disease (unstable angina, s/p myocardial infarction ≤1 month); respiratory disease (advanced COPD or pulmonary fibrosis); uncontrolled hypertension; active systemic infection; or psychiatric illness/social situations that would limit compliance with study requirements.
11. Certain medicines and herbal remedies (see Appendix B) taken during the 7 days before the start of study drug.
 12. A history of cancer >3 years from the time of enrollment, and the patient is not up to date with surveillance for that cancer (based on national guidelines), or has evidence of cancer at the time of enrollment.

1.6 Trial design and methods

Patients will be randomised (1:1 ratio) to receive either 25 mg YF476 or matching placebo. They will attend the clinic 4 or 5 times, and will take up to 18 weeks to complete the trial.

At **Visit 1**, patients will sign the Informed Consent form. Patients will undergo assessment of eligibility, physical examinations, ECG, urine pregnancy test (pre-menopausal women only) and safety tests of blood and urine.

Visit 2 can take place on the same day as visit 1, or up to 2 weeks later. At Visit 2, patients will undergo ECG, safety tests of blood and urine, including urine pregnancy test (pre-menopausal women only), unless Visit 2 is on the same day as Visit 1. All patients will have baseline biomarker assessments, baseline esophagogastroduodenoscopy (EGD) and biopsies. If they meet all the eligibility criteria, they will be given a bottle of study medication (25 mg YF476 or placebo) capsules to take once daily, with breakfast, starting the next day. Patients will complete a diary card throughout the treatment period.

The Week 6 visit will be 6 weeks after starting study treatment. Patients will fast before the visit, and will bring their dose of study medication to the clinic, to take after fasting blood tests. First, patients will have safety tests of blood and urine, ECG, and blood taken for biomarkers and trough YF476 concentration. Patients will then take their study medication, and 1 h afterwards will have blood taken for peak YF476

concentration. Patients will be asked about any adverse events and concomitant medications, and will return their study medication bottle for assessment of compliance. They will receive their next bottle of study medication.

The Week 12 visit will be 12 weeks after starting study treatment. Patients will fast before the visit, and will bring their dose of study medication to the clinic, to take after fasting blood tests. First, patients will have safety tests of blood and urine, ECG, and blood taken for biomarkers and trough YF476 concentration, before undergoing EGD assessments and biopsies. Patients will then take their study medication, and 1 h afterwards will have blood taken for peak YF476 concentration.

Follow-up visit will be 4 weeks after the patients have stopped taking study medication. Patients will have safety tests of blood and urine, ECG, and blood tests for biomarkers. Patients will be asked about any adverse events.

1.7 Methods

- Esophagogastroduodenoscopy (EGD), to enable taking of biopsies for assessment of the primary endpoint, Ki67 expression levels;
- blood sampling for assay of biomarkers and serum for storage;
- diary card for patients to record adverse events, concomitant medication and compliance; and
- physical examination, ECG and safety tests of blood and urine.

1.8 Primary variable

Efficacy: change in Ki67 expression between baseline (Visit 2) and the Week 12 visit

1.9 Secondary variables

Biomarkers: change from baseline at Week 12 in biomarkers potentially associated with esophageal adenocarcinoma, in particular, cyclooxygenase-2 (COX-2), P53, CCK2R and DCAMKL1, and in fasting serum gastrin and plasma CgA

Safety: vital signs, ECG, physical examination, laboratory safety tests: blood tests: red blood cells (RBC), haemoglobin, haematocrit, platelets, white blood cells (WBC, differential: neutrophils, bands, lymphocytes, monocytes, eosinophils, basophils), sodium, potassium, magnesium, chloride, bicarbonate, creatinine, serum glucose, blood urea nitrogen (BUN), alkaline phosphatase, lactate dehydrogenase (LDH), serum glutamic-oxaloacetic

transaminase/aspartate amino transferase (SGOT/AST), serum glutamic-pyruvic transaminase/ alanine aminotransferase (SGPT/ALT), total bilirubin, total protein, albumin, calcium, amylase, lipase; and urine tests: pH, specific gravity, protein, glucose, ketones, blood, and change in histology.

Tolerability: adverse events

Pharmacokinetics: trough and peak concentrations of YF476

[figure not shown]
STUDY DIAGRAM**Randomized, placebo-controlled trial of a gastrin receptor antagonist, YF476, in Barrett's esophagus**

Table of contents

Signatures	5
1 Summary	6
1.1 Background	6
1.2 Trial medication	6
1.3 Objectives	6
1.4 Type of trial	7
1.5 Trial population	7
1.6 Trial design and methods	9
1.7 Methods	10
1.8 Primary variable	10
1.9 Secondary variables	10
Table of contents	13
List of Abbreviations	16
2 Objectives	19
2.1 Primary objective	19
2.2 Secondary objectives	19
3 Background	19
3.1 Barrett's esophagus	19
3.2 YF476	20
3.2.1 Non-clinical studies	20
3.2.2 Phase 1 studies	21
3.3 Rationale	22
4 Summary of study plan	23
4.1 Study design	23
4.2 Discussion of study design	24
4.3 Risk-benefit analysis	25
5 Patient selection	26
5.1 Inclusion criteria	26
5.2 Exclusion criteria	27
5.3 Inclusion of women and minorities	28
5.4 Recruitment and retention plan	28
6 Administration of study medication	29
6.1 Dose regimen and dose groups	29
6.2 YF476 administration	29
6.3 Run-in procedures	29

6.4	Contraindications	29
6.5	Concomitant medications	30
6.6	Dose modification	30
6.7	Compliance	30
7	Pharmaceutical information	32
7.1	Active pharmaceutical ingredient (API): YF476	32
7.2	Formulated intermediate: spray-dried YF476	32
7.3	Final formulation	33
7.4	Packaging and labelling	33
7.5	Storage, accountability and dispensing of study medication	33
7.6	Registration and randomization	34

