The pharmacokinetic profile of YF476 varied among the 1996, 2001, 2005 and 2009 capsule formulations. The 2001 and 2005 formulations were crystalline, and the 1996 and 2009 formulations were spray-dried. The spray-dried formulations had the most favourable profile. In a single-dose study of 50–400 mg of the current (2009) formulation of YF476, absorption was rapid, T_{max} was 1.5–2 h, $T_{1/2}$ varied with dose, and C_{max} and AUC_{0-24} were not proportional to dose. $T_{1/2}$ after 100 mg YF476 was about 7 h. Food increased C_{max} and AUC_{0-24} by 1.9 and 1.6-fold, respectively. The absolute bioavailability was about 16% in a study of 100 mg 'cold' YF476 by mouth after fasting and 15 μ g ^{14}C -YF476 intravenously. Protein binding in human serum was about 84%. In a 7-day study of 100 mg YF476 twice daily of the 1996 formulation, YF476 reached steady state by Day 3 and did not accumulate by Day 7. Even though the crystalline formulations were much less bioavailable than the spray-dried formulations, the pharmacodynamic results were still favourable, which suggests that YF476 is a potent gastrin antagonist in man.

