4.1 Study design

We propose a randomized, double-blind, placebo-controlled pilot study of YF476, a cholecystokinin-2 receptor antagonist, in patients with Barrett's esophagus without dysplasia. Patients will take YF476 or placebo for 12 weeks.

There are 2 research sites, Columbia University and the University of Cambridge. We aim for 20 patients to complete the study. Patients will be randomized (1:1 ratio) to treatment with YF476 or placebo.

Patients will make up to 5 visits to the research site (Visits 1 and 2 may be combined, or up to 2 weeks apart. See schedule of events in Section 8.1.):

- Registration (Visit 1)
- Baseline (Visit 2 – start of treatment phase)
- Study treatment (6 weeks after the start of the treatment phase).
- End of study treatment (after 12 weeks' treatment)
- Follow-up (4 weeks after the end of treatment).

After giving informed consent (Visit 1) and after the initial endoscopy (Visit 2), patients will be given one bottle of YF476 or placebo. They will be given a study bottle again at the Week 6 visit.

The primary endpoint of the study (Ki67 expression) will be assessed using endoscopic biopsies taken at baseline and at 12 weeks.

Esophageal tissue from endoscopic biopsies will be evaluated for Ki67 expression (primary endpoint) and expression of additional markers potentially associated with

esophageal neoplasia (secondary endpoints). Expression of these markers will be assessed by RNA sequencing (RNA-Seq), immunohistochemistry (IHC) and reverse transcriptase-PCR (RT-PCR), as appropriate.

Blood samples will be taken at Visit 2, the Week 6 visit and the Week 12 visit for measurement of serum gastrin and plasma CgA, and at the Week 6 and Week 12 visits for trough and peak YF476 concentrations.

Safety tests and pregnancy tests (pre-menopausal women only) will be done at each visit. Patients will complete a diary card daily to record study drug, concomitant medication and adverse events. Adverse events will be assessed 6 and 12 weeks after starting study medication, and 4 weeks after finishing study medication. Blood and urine samples will also be collected at these visits to assess for hematologic, metabolic, or other disturbances that may be due to study drug. The duration of the study for each individual patient will be between 16 and 18 weeks.

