8.3 Evaluations during study treatment

Week 6 visit: after 6 weeks of study treatment

The investigator will:

- check that the patient has fasted;
- collect the diary card, and issue a new one;
- check the diary card for compliance with treatment, and for adverse events and concomitant medication;
- collect the study medication bottle and assess compliance;
- do an ECG and vital signs;
- take blood and urine for laboratory safety tests and urine pregnancy testing (pre-menopausal women only);
- take blood samples for fasting serum gastrin, plasma CgA, trough YF476 concentration and serum for storage;
- after taking the fasting blood samples, give the patient their dose of study medication, wait 1 h, then collect blood for assay of peak concentration of YF476;
- issue a new container of study medication, to be taken as before;
- remind the patient to fast before the next visit; and
- remind the patient not to take their study medication at home on the day of the Week 12 visit, but instead to bring their container of study medication with them to the visit, and take their dose at the clinic, after the fasting blood tests and endoscopy.

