13.4 Efficacy Analyses

All efficacy analyses, summaries and listings will be generated using the efficacy analysis set.

Primary efficacy variables are:

- Change in Ki67 expression (ΔKi67)

Secondary efficacy variables are:

- Changes in gene expression in BE tissue (measured by RNA-Seq).
- Change in CCK2R mRNA levels (measured by qRT-PCR)
- Change in DCAMKL1 expression (measured by IHC)
- Change in DCAMKL1 mRNA levels (measured by qRT-PCR)
- Change in COX-2 mRNA levels (measured by qRT-PCR)
- Change in p53 expression (measured by IHC)
- Change in serum gastrin and plasma CgA between baseline and Visit 5

For all efficacy variables listed above, individual values will be presented by patient and summarised by visit.

The primary endpoint (Change from baseline (Visit 2) in Ki67 expression (Δ Ki67)) will be summarised using descriptive statistics. The primary analysis for the primary endpoint will use two sample t-tests comparing between treatment groups. Nominal p-value and 95% confidence intervals for treatment difference will be reported.

To evaluate the robustness of the primary analysis, the following sensitivity analysis will also be performed:

Baseline Adjusted Analysis: this sensitivity analysis will use an analysis of covariance model with the primary endpoint as the dependent variable, treatment group as a factor and baseline (Visit 2) as a covariate. Adjusted least square means and corresponding 95% confidence interval will be reported.

Serum gastrin and chromogranin A (CgA) will be measured at baseline (Visit 2) and at Weeks 6 and 12. Analyses will be performed to determine whether there is a correlation between baseline gastrin and subsequent Δ Ki67. YF476 assays will be performed at Weeks 6 and 12.

Analysis of the secondary endpoints will be similar to the primary analysis. No sensitivity analysis is planned for these endpoints.

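### Serum gastrin and plasma CgA: the protocol gives two conflicting time points, and no planned between-arm estimate uses both on-treatment samples or adjusts for baseline

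*Protocol*

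**What the plan says.** **Time point.** Protocol 1.9 places gastrin and CgA in one sentence with the tissue markers: "change from baseline at Week 12 in biomarkers potentially associated with esophageal adenocarcinoma", and then "and in fasting serum gastrin and plasma CgA". Protocol 13.4 lists the variable as "Change in serum gastrin and plasma CgA between baseline and Visit 5". Protocol 4.1 says "Patients will make up to 5 visits to the research site" and lists registration, baseline, Week 6, Week 12 and follow-up in that order. The SAP shells for PK and compliance label their on-treatment visits 3 and 4. Visit 5 is therefore the follow-up, four weeks after treatment stops.

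**Samples.** Protocol 13.4 states "Serum gastrin and chromogranin A (CgA) will be measured at baseline (Visit 2) and at Weeks 6 and 12". Protocol 8.3 has the investigator "take blood samples for fasting serum gastrin, plasma CgA, trough YF476 concentration and serum for storage" at Week 6, before that day's dose, and 8.4 repeats this at Week 12. Sections 8.1 and 8.5 add an off-drug sample at follow-up. Biopsies are taken only at baseline and Week 12.

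**Analysis in the protocol.** "Analysis of the secondary endpoints will be similar to the primary analysis". The primary analysis is a two-sample t-test on the change score. The baseline-adjusted ANCOVA is a sensitivity analysis for the primary endpoint only, and 13.4 excludes sensitivity analyses for the secondary endpoints. Section 13.2 uses observed data only.

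**Analysis in the SAP.** SAP 3 brings gastrin and CgA within its scope. SAP 10 names netazepide versus placebo as the comparison of interest, but SAP 4.3 plans no formal testing. SAP 15 summarises values and changes by arm and visit, with mean profile plots. The assigned shell, T_EG2, has no column for a between-arm difference or its interval. SAP 17 records one change from the protocol, to the PK set.

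**The concern.** Gastrin and CgA are a named secondary objective and the blood-based evidence that the drug acts in patients already on long-term PPIs. As written, a programmer cannot tell whether the comparison is on drug (Week 12) or off drug (Visit 5). The protocol's t-test has disappeared from the SAP without being declared, although Protocol 13.2 says that deviations will be described there and SAP 3 says substantial differences will be identified.

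With about 10 patients per arm, a second on-treatment sample and the baseline value could both sharpen the estimate of the arm difference. No planned between-arm contrast uses them that way. A patient with Week 6 but no Week 12 blood would meet the ITT definition, which needs one post-baseline assessment, yet would contribute nothing to a Week 12 comparison.

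**Working it through.** **1. The plan's own figure.** The only power figures are for Ki67 (Protocol 13.7, Table 1: 10 per arm, two-sided 0.05). The noncentral t with 18 df reproduces all nine cells. For example, it gives 97.7% against 98% stated (difference 0.30, SD 0.16), 96.5% against 97% (0.25, 0.14), 91.0% against 91% (0.25, 0.16) and 83.6% against 84% (0.25, 0.18). The same calculation is used in step 4.

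**2. Assumptions.** Neither document gives an SD or a within-patient correlation for gastrin or CgA. Assume equal variances at all visits. Let b be the correlation of each on-treatment value with baseline (0.3 to 0.7) and p the correlation between Weeks 6 and 12 (0.5 to 0.9).

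**3. Variance, in units of the common variance.**

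- Week 12 minus baseline: 2(1 − b).
- Mean of Weeks 6 and 12, minus baseline: (1 + p)/2 + 1 − 2b.
- Ratio: 1 − (1 − p)/[4(1 − b)], so the saving is (1 − p)/[4(1 − b)].

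If p = b, the saving is 1/4 whatever the correlation. The SE ratio is √0.75 = 0.866, so the SE is 13% smaller, or equivalently the Week 12 interval is 1/0.866 − 1 = 15% wider. This equals 10/0.75 = 13.3 patients per arm instead of 10.

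If p exceeds b, the saving is smaller. The break-even column is explained in step 5.

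| b | p | saving | break-even share |
|---|---|---|---|
| 0.3 | 0.5 | 0.5/2.8 = 17.9% | 81% |
| 0.3 | 0.7 | 0.3/2.8 = 10.7% | 89% |
| 0.3 | 0.9 | 0.1/2.8 = 3.6% | 96% |
| 0.5 | 0.7 | 0.3/2.0 = 15.0% | 84% |
| 0.5 | 0.9 | 0.1/2.0 = 5.0% | 95% |
| 0.7 | 0.9 | 0.1/1.2 = 8.3% | 92% |

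The saving moves back towards 25% as p approaches b. Under serial correlation, where Week 12 is less correlated with baseline than Week 6 is, it is 33% to 37% for adjacent-visit correlations of 0.5 to 0.9.

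**4. Power for the protocol's t-test, with p = b and the same effect at both visits.** An effect of 1.325 SD of the change score has 80% power at Week 12 alone. With the average it becomes 1.325/0.866 = 1.53 SD, with 90% power. For a 1 SD effect, 56% becomes 69%.

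**5. When averaging helps.** If the Week 6 effect is a share f of the Week 12 effect, averaging gains power only when (1 + f)/2 exceeds the square root of the variance ratio, that is f > 2√ratio − 1. With equal correlations this is 2(0.866) − 1 = 73%. It rises to 96% at b = 0.3, p = 0.9.

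**6. Baseline as a covariate.** At Week 12 alone, ANCOVA has variance 1 − b² against 2(1 − b) for the change score, a ratio of (1 + b)/2. That is 0.75 at b = 0.5, 0.85 at 0.7 and 0.95 at 0.9. This gain does not depend on Week 6.

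**The case against.** The strongest reply is that the SAP plans no test and shows Weeks 6 and 12 in the same way, so nothing planned there loses power. That stands in part: the power figures above describe the protocol's t-test only. It does not remove the conflict between 1.9 and 13.4, the undeclared change, or the absence of any estimate of the comparison that SAP 10 names.

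A reader might go further and infer that the plan throws away a quarter of the attainable precision. The documents do not support this. A quarter holds only under equal correlations and a stable effect, and no figure for these markers is given. A saving as high as 42% would need the two on-treatment values to correlate less with each other (0.5) than with baseline (0.7).

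A reader might also infer that both visits lie on a plateau. Protocol 3.2.2 says "YF476 reached steady state by Day 3 and did not accumulate by Day 7", but that is exposure, from a 7-day study of 100 mg twice daily of the 1996 formulation. The 6-week CgA result is from healthy subjects given 100 mg daily. The same section reports that the effect on gastric pH was mostly lost on repeated dosing. None of the human data cited there runs past 6 weeks. Stability from Week 6 to Week 12 is suggested, not shown.

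Week 12 is also a defensible endpoint: it is the end of treatment and matches the Ki67 visit. Making the average the headline would change what is estimated. The missing-sample risk is limited too. Patients who stop drug are followed where possible (8.7.1), withdrawals may be replaced (5.4), and enrolment runs until 20 patients have had the Week 12 endoscopy (8.8).

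**Conclusion.** The point holds as a conflict between passages plus a modest efficiency gain. The time points in Protocol 1.9 and 13.4 disagree, the SAP drops the protocol's between-arm test without listing it in SAP 17, and no planned contrast uses both on-treatment samples or takes baseline as a covariate.

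The size rests on assumed correlations. The average has 25% less variance than the Week 12 change when correlations are equal, and about 4% to 18% less over the tabulated cases where the on-treatment values are closer to each other than to baseline. It improves power only if the Week 6 effect is at least about 73% of the Week 12 effect, and up to about 96% in those cases. The documents do not justify replacing Week 12 by the average, and the primary analysis is unaffected.

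**What to change.** 1. Reconcile Protocol 1.9 and 13.4 so that one visit defines the gastrin and CgA variable. Keep Week 12 as the stated endpoint and refer to visits by week rather than number.
2. In Protocol 13.4 and SAP 15, for these two markers only, estimate the between-arm difference with a 95% CI from one repeated-measures model: treatment, visit (Weeks 6 and 12), treatment by visit, and baseline as a covariate. With two visits, an unstructured covariance has only three parameters.
3. Report the Week 12 contrast first, with the Week 6 contrast and the Week 6/12 average beside it. The variance saving in step 3 belongs to the average. The Week 12 contrast gains from baseline adjustment and from keeping patients with one visit missing.
4. In SAP 17, state how this differs from the protocol's t-test. In SAP 4.3, say whether the interval is for estimation only. Add a between-arm column to the table shell.
5. Leave the tissue markers at Week 12 and the follow-up sample descriptive.

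The cost is a few lines of text, one model and one shell, with no new visits or samples. The downside is that the average is diluted if the effect is still growing after Week 6, which the separate contrasts would show. The change should be made before the SAP is finalised and the code broken.
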